9.2 Methods of Assessment

A T-DOC® 5 French air-charged catheter will be used to assess and record bladder and abdominal pressures which are in turn used by the clinician to identify urodynamic events. These measurements will be recorded using a LABORIE urodynamics system. The resulting interpretations regarding safety, effectiveness, and usability will be made by the physician overseeing the subject’s case. Patients capable of providing feedback regarding their level of discomfort experienced during the procedure with the T-DOC® 5Fr vesical and abdominal catheters will be presented with copies of the Wong-Baker scale from 0 (“No Hurt”) to 10 (“Hurts worst”) and asked questions by clinic staff who will record their responses on form TDOC5Fr-PEDS-01-CRF4. Subjects will respond to the questions on a scale of 1 through 10.

All study outcome data captured will be compiled and analysed by the LABORIE study team to determine if the endpoints were successfully achieved based on whether the null hypotheses were accepted or rejected.

10 SUBJECT SAFETY

10.1 Definitions

10.1.1 Adverse Events:

Any untoward medical occurrence in a subject, whether or not related to the investigational medical device.

10.1.2 Adverse Device Effect:

Any adverse event related to the use of an investigation medical device.

10.1.3 Device Deficiency:

Inadequacy of a medical device with respect to its identity, quality, durability, reliability, safety or performance

10.1.4 Serious Adverse Event:

An adverse event that:

1. Led to a death;
2. Led to a serious deterioration in health of a subject, user, or others that:
 - a. Results in a life-threatening illness or injury;
 - b. Results in a permanent impairment of a body structure or body function;
 - c. Requires in subject hospitalization or prolongation of existing hospitalization;
 - d. Results in medical or surgical intervention to prevent life-threatening illness or injury or permanent impairment to body structure or a body function;
3. Led to foetal distress, foetal death or a congenital abnormality/birth defect.

10.1.5 Unanticipated Adverse Device Effect:

Any serious adverse effect on health or safety or any life-threatening problem or death caused by, or associated with, a device, if that effect, problem, or death was not previously identified in nature, severity, or degree of incidence in the investigation protocol or application, or any other unanticipated serious problem associated with a device that relates to the rights, safety, or welfare of subjects.

10.1.6 Unanticipated Serious Adverse Device Effect (USADE):

Serious adverse device effect which by nature, incidence, severity or outcome has not been identified in the current version of the risk analysis report.

10.2 Data Collection

Adverse events, device deficiencies, serious adverse events, and unanticipated adverse device effect shall be recorded on the CRF.

10.3 Reporting

All serious adverse events and unanticipated adverse device effects occurring during the investigation will be reported as soon as possible, but no later than 10 working days after the Investigator/Laborie first learns of the effect. This information will be submitted to Laborie/investigator and the IRB.

10.4 Foreseeable Events

For a complete Risk Management Report please refer to the Risk Management File. The residual risks have been deemed acceptable and the benefits outweighs the risks. Please also refer to Section 4.4 above Assessment of Risks and Adverse Device Effects

10.6 Follow-Up

If an adverse event occurs, any follow-up intervention prescribed is at the discretion of the Investigator, and the site must notify Laborie of the outcome of the follow-up. The study safety endpoint will be measured by capturing adverse event data both during the study visit, and at 5-7 days post-test follow-up.

11 STUDY PROCEDURE

11.1 Visit Schedule

Evaluation	Screening & Clinic Visit	Follow-up
	Day 1	Day 5-7
Informed Consent & Assent	X	
Inclusion Criteria	X	
Exclusion Criteria	X	
Record any Adverse Events	X	X

Questionnaire for Operator (once minimum 3 subjects completed)		X
--	--	---

11.2 Screening for Eligibility

Subject's may be screened for eligibility for this study by referencing the inclusion criteria. No special testing is required in order to determine eligibility.

11.3 Day 1 (Screening & Clinic Visit)

1. Determine if the subject is eligible for this study.
2. Conduct Informed Consent and Assent discussion with the subject and guardian and sign where required.
3. Collect medical history and record in case report form (TDOC5Fr-PEDS-01-CRF2).
4. Collect and record other patient details as required on TDOC5Fr-PEDS-01-CRF1 [weight (lbs), height (',"), date of birth, sex, etc].
5. Site personnel will explain what will happen during the urodynamics test to the subject/parent or caregiver.
6. Site personnel will prepare urodynamics equipment, study materials, other sterile disposables and supplies as required for the urodynamic study and record catheter lot number information on TDOC5Fr-PEDS-01-CRF1.
7. Follow the investigational device instructions for use for placing the catheters. Record insertion depth once catheter is in place on TDOC5Fr-PEDS-01-CRF1.
8. Conduct urodynamic study according to Good Urodynamic Practice recommendations, including regular cough checking to ensure good pressure transmission and catheter positioning wherever possible (Rosier *et al.*, 2016).
9. If within capabilities of the child, and if their condition allows, complete TDOC5Fr-PEDS-01-CRF4 – Subject Questionnaire.

11.4 Day 5-7 (Follow-Up)

1. Site personnel will telephone the subject's guardian/caregiver and inquire about any adverse events that occurred after Visit 1 that may or may not be persistent. Record the call details on the subjects' CRF (TDOC5Fr-PEDS-01-CRF1).

NOTE: If an adverse event occurs during this study, any follow-up intervention prescribed is at the discretion of the Investigator. Each subject will be contacted 5-7 days post-test in order to record the occurrence of any adverse events. Any subject with persistent symptoms post-test shall be followed until such a time it is resolved, and the site must notify Laborie of the

outcome of the follow-up. This information should also be recorded on the subject's CRF (TDOC5Fr-PEDS-01-CRF1).

11.5 End of Study (EOS)

At the conclusion of the urodynamics test, the subject is no longer required to undergo any further study-related procedures, with the exception of a 5-7 day telephone follow-up.

Once a clinical user has performed a minimum of 3 urodynamic studies and the related tasks under this protocol, they are then eligible to complete the Usability Questionnaire (TDOC5Fr-PEDS-01-CRF3).

Once a site has completed its' target recruitment, the sponsor (Laborie) will schedule a time to close-out the site, either in person or by telephone as per Section 14.1. All study related files will be collected and reviewed for completeness. Final arrangements will be discussed regarding payment at this point in time. The EOS is considered the point when all subjects have been followed-up and data collection completed.

12 STATISTICAL CONSIDERATIONS

12.1 Primary Endpoint

In order to satisfy the primary endpoint, each subject CRF will include a binomial question regarding clinician acceptance of the device as being both safe and effective. According to the risk determination outlined in section 4.4 Assessment of Risks and Adverse Device Effects, no more than minimal risk is foreseen for the subject by participating in this study. Given this, the allowable Type I error (α) will be 5% (1-confidence), such that the clinician will grade the device as being safe and effective for 95% of subjects enrolled in this study. Whereas the corresponding Type II error is estimated at 10% (reliability). As stated earlier, safety and effectiveness will be evaluated separately via the following sets of hypotheses:

12.1.1 Primary Hypothesis Test for Safety

H_0 : Clinicians rate T-DOC® 5 Fr vesical and abdominal catheter as safe for measuring urodynamic pressure in 95% of enrolled pediatric subjects

H_a : Clinicians rate T-DOC® 5 Fr vesical and abdominal catheter as safe for measuring urodynamic pressure in less than 95% of enrolled pediatric subjects

12.1.2 Primary Hypothesis Test for Effectiveness

H_0 : Clinicians rate T-DOC® 5 Fr vesical and abdominal catheter as effective for measuring urodynamic pressure in 95% of enrolled pediatric subjects

H_a : Clinicians rate T-DOC® 5 Fr vesical and abdominal catheter as effective for measuring urodynamic pressure in less than 95% of enrolled pediatric subjects

In both cases, analysis of the clinical results will be performed as outlined below based on a binomial distribution. In general, the probability mass function of a binomial random variable X is:

$$f(x) = \binom{n}{x} p^x (1-p)^{n-x}$$

In this study, n represents the number of patients accepted into the trial; x represents the number of procedures for which clinicians rate the device as safe or effective (as the case may be); and $p = 0.95$ (as stated in the null hypothesis that 95% of the time clinicians rate the device as safe or effective as the case may be).

Because the alternative hypotheses are directionally based, the null hypotheses will be accepted or rejected based on one-tailed tests. If the numbers of patients accepted into the trial is 28 as expected (see section 12.2 Sample Size Determination & Power), the test statistic, for both one-tailed tests with an $\alpha = .05$, will be:

$$P(\text{true } X \leq x) = \binom{28}{x} 0.95^x (1 - 0.95)^{28-x} \leq 0.05$$

Solving for x in the case of 28 patients results in the null hypothesis being rejected when 24 procedures or fewer are rated as safe and accepted when 25 or more procedures have been rated safe. The actual results will be tabulated based on the actual number of patients accepted into the study.

12.2 Secondary Endpoint

To satisfy the secondary (usability) endpoint, a categorical response variable using a defined ordinal data scale will be used. At least 80% of clinical users, who have performed three or more procedures with subject device, shall rate the T-DOC® 5 Fr catheter usability performance as 3.0 or better (on a scale of 1-5) for the clinical user questionnaire, comparing their experience with use of their currently used urodynamics catheter. For this endpoint, eligible clinicians will respond to the questions on a scale of 1 through 5. To enable analysis based on a Binomial Distributions, responses of 3, 4, or 5 will be tallied as a positive result while responses of 1 or 2 will be tallied as a negative result. However, because the number of clinicians who perform three procedures or more with the T-DOC® 5 Fr vesical and abdominal catheter during this study is anticipated to be small (≤ 5), the results will be reported based on the confidence of 95% (based on the assumed minimal risk level described in section 4.4) and the calculated reliability permitted by the actual sample size achieved (i.e., count of eligible clinicians). The following hypothesis test case will be used to evaluate clinical study results.

H_0 : 80% of clinicians rate T-DOC® 5 Fr vesical and abdominal catheter usability performance as 3 or better compared to their experience with their currently used urodynamics catheter.

H_a : Less than 80% of clinicians rate T-DOC® 5 Fr vesical and abdominal catheter usability performance as 3 or better compared to their experience with their currently used urodynamics catheter.

The probability mass function of a binomial random variable X stated above will again be used to analyse the questionnaire data. For the secondary endpoint, n represents the number of clinicians who performed three or more procedures with the T-DOC® 5 Fr vesical and abdominal catheter; x represents the number of procedures for which the eligible clinicians rate the device usability performance as 3 or better compared to their experience with their currently used urodynamics catheter; and $p = 0.8$ (as stated in the null hypothesis that 80% of the time clinicians rate the device usability performance as 3 or better compared to their experience with their currently used urodynamics catheter).

Again, because the alternative hypothesis is directionally based, the null hypotheses will be accepted or rejected based on a one-tailed test. For example, if the numbers of clinicians eligible to complete a questionnaire is 5, the test statistic, for the one-tailed tests, with an $\alpha = .05$ will be:

$$P(\text{true } X \leq x) = \binom{5}{x} 0.8^x (1 - 0.8)^{5-x} \leq .05$$

Again, if it is assumed that 5 clinicians respond to the questionnaire, the reliability level would be 55% (see Section 12.5 Sample Size Determination and Power). Solving for x based on this assumption would then result in the null hypothesis being rejected when 1 or fewer clinicians rate the T-DOC® 5 Fr vesical and abdominal catheter usability performance as 3 or better compared to their experience with their currently used urodynamics catheter and accepted when 2 or more clinicians rate the T-DOC® 5 Fr vesical and abdominal catheter usability performance as 3 or better compared to their experience with their currently used urodynamics catheter.

Alternatively, a second calculated confidence and reliability level combination could be 80% and 70%, respectively, based on 5 clinicians responding to the questionnaire. In this case, if the numbers of clinicians eligible to complete a questionnaire is 5, the test statistic, for the one-tailed tests, with an $\alpha = 0.2$ (i.e., 1-confidence level) will be:

$$P(\text{true } X \leq x) = \binom{5}{x} 0.8^x (1 - 0.8)^{5-x} \leq .2$$

Solving for x would result in the null hypothesis being rejected when 2 or fewer clinicians rate the T-DOC® 5 Fr vesical and abdominal catheter usability performance as 3 or better compared to their experience with their currently used urodynamics catheter and accepted when 3 or more clinicians rate the T-DOC® 5 Fr vesical and abdominal catheter usability performance as 3 or better compared to their experience with their currently used urodynamics catheter.

Due to the minimal risk of the device as stated in section 4.4, the study team has opted to use a combination of levels where the confidence level is stated as 95% (i.e., $\alpha = 0.05$), and the reliability (power) of the test will be calculated, though it will likely be significantly reduced.

The actual results will be tabulated based on the actual number of clinicians who respond to the questionnaire.

12.3 Exploratory Endpoint

12.3.1 Exploratory Hypothesis Test for Discomfort/Pain

To satisfy the first exploratory endpoint (subject experience), a categorical response variable using the Wong-Baker scale from 0 (“No Hurt”) to 10 (“Hurts worst”) will be used. The stated exploratory endpoint is that 95% of patients capable of providing feedback on a Visual Analogue Scale, will grade their discomfort/pain of 5 or lower, on the Wong-Baker scale from 0 (“No Hurt”) to 10 (“Hurts worst”). To enable analysis based on a Binomial Distributions, responses of 1, 2, 3, 4, or 5 will be tallied as a positive result while responses of 6, 7, 8, 9, or 10 will be tallied as a negative result. Additionally, grouping the data in this manner is assumed to minimize much of the variation caused by the nature of subjective feedback from pediatric subjects. A confidence level of stated as 95 % (i.e., $\alpha = 0.05$) has been selected based on the risk determination that no more than minimal risk is foreseen for the subject by participating in this study (4.4 Assessment of Risks and Adverse Device Effects). As stated earlier, the following hypothesis test case will be used to evaluate the exploratory clinical study results.

H_0 : 95% or more of subjects capable of providing feedback on a Visual Analogue Scale, will grade their discomfort/pain experienced experience during the procedure utilizing the T-DOC® 5 Fr vesical and abdominal catheter at 5 or lower, on the Wong-Baker scale from 0 (“No Hurt”) to 10 (“Hurts worst”).

H_a : Less than 95% of subjects capable of providing feedback on a Visual Analogue Scale, will grade their discomfort/pain experienced experience during the procedure utilizing the T-DOC® 5 Fr vesical and abdominal catheter at 5 or lower, on the Wong-Baker scale from 0 (“No Hurt”) to 10 (“Hurts worst”).

The subjects will be presented with copies the Wong-Baker scale from 0 (“No Hurt”) to 10 (“Hurts worst”) and asked to respond to the questions by clinic staff who will record their responses on TDOC5Fr-PEDS-01-CRF4. As with the previous endpoints, the alternative hypothesis is directionally based, therefore, the null hypothesis will be accepted or rejected based on a one-tailed test. Because the subjects range in age from 2-12 years, the number of subjects capable of providing feedback on the Wong-Baker scale is anticipated to be limited (≤ 14). Similar to the secondary hypothesis, the study team has opted to use a combination of levels where the confidence level is stated as 95% (i.e., $\alpha = 0.05$), and the reliability (power) of the test will be calculated, based on the sample size achieved (i.e., count of subjects capable of

providing feedback on the Wong-Baker scale). See section 12.5 Sample Size Determination and Power for further details.

The probability mass function of a binomial random variable X as stated for the primary and secondary endpoints will again be used to analyse the subjects' questionnaire data. For the exploratory endpoint, n represents the number of subjects capable of providing feedback on the Wong-Baker scale; x represents the number of subjects who rate their discomfort/pain experienced during the procedure utilizing the T-DOC® 5 Fr vesical and abdominal catheter at 5 or lower on the Wong-Baker scale from 0 ("No Hurt") to 10 ("Hurts worst"); and $p = 0.95$ (as stated in the null hypothesis that 95% of subjects capable of providing feedback on a Visual Analogue Scale, will grade their discomfort/pain experienced experience during the procedure utilizing the T-DOC® 5 Fr vesical and abdominal catheter at 5 or lower).

Again, because the alternative hypothesis is directionally based, the null hypotheses will be accepted or rejected based on a one-tailed test. For example, if the numbers of subjects capable of responding to the questionnaire is 10, the test statistic, for the one-tailed tests, will be:

$$P(\text{true } X \leq x) = \binom{14}{x} 0.95^x (1 - 0.95)^{14-x} \leq 0.05$$

Again, if it is assumed that 14 subjects respond to the questionnaire, the reliability level would be approximately 80% (see Section 12.5 Sample Size Determination and Power). Solving for x , with the assumed count of subjects would result in the null hypothesis being rejected when 12 or fewer subjects capable of providing feedback on a Visual Analogue Scale, grade their discomfort/pain experienced experience during the procedure utilizing the T-DOC® 5 Fr vesical and abdominal catheter at 5 or lower, on the Wong-Baker scale from 0 ("No Hurt") to 10 ("Hurts worst").

The actual results will be tabulated based on the actual number of subjects who respond to the questionnaire.

12.3.2 Exploratory Data Collection regarding influencing factors on insertion depth

To satisfy the second exploratory endpoint, subject data including gender, age, height, weight, adverse events during or immediately following the test and 5-7 days follow-up, catheter insertion depth will be collected as objective evidence on each patient's CRF, where insertion depth is considered the response variable and assumed to be influenced by gender, age, height, weight and/or BMI. Adverse event data will be factored into the assessment of the adequacy of the individual insertion depth used during the subject's procedure.

The collected data will be reported using graphical tools for central tendency and dispersion of insertion depths based on gender, age, height, weight, and BMI. The goal of reporting data in this manner is to facilitate the identification of a natural subject stratification approach for use in later research regarding optimal insertion depth.

Based on the stated data collection and analysis approach, the anticipated outcome of this endpoint, and the fact that the subject population is not being controlled for age, height, or weight, this study exploratory objective is being evaluated as a case-series observational study. Accordingly, sample size will not be pre-determined based on pre-ordained confidence and reliability statements.

12.4 Sample Size Determination & Power

Sample size calculations were and will be performed in accordance with Binomial Distribution theory (except for the second exploratory objective), utilizing the following formula:

$$n = \frac{\ln(1 - \text{confidence level})}{\ln(\text{reliability})}$$

Where n is the number of samples (e.g., patients, clinicians), and \ln is natural log. In the case of the primary endpoint, the desired confidence level and reliability have been stated as 95% and 90% respectively. Hence the minimum required number of samples for the primary endpoint is 28 as shown below.

$$n = \frac{\ln(1-0.95)}{\ln(0.90)} = 28$$

In addition, the study sponsor will allow up to 33 subjects (20% additional) during the allowable recruitment time period given the minimum recruitment goals are met (see Section 6.1 for and Section 7.1 for stratification and recruitment requirements). The additional subjects will ensure that the desired confidence and reliability levels are met should any data or subjects be disqualified due to technical errors or if any subject requests to exit the study.

In the case of the secondary endpoint, the confidence level has been stated to be 80% and the reliability statement will be calculated based on the actual number of clinicians who respond to the questionnaire. For instance, if 5 clinicians respond to the questionnaire, and an $\alpha = 0.20$ (i.e., (1- confidence level)) is maintained, the reliability of this test will drop to approximately 73%.

In the case of the first exploratory endpoint, the confidence level has been stated to be 95% and the reliability statement will be calculated based on the actual number of subjects who respond to the questionnaire. For instance, if 14 subjects respond to the questionnaire, and an $\alpha = 0.05$ (i.e., (1- confidence level)) is maintained, the reliability of this test would be approximately 80%.

In all cases, test statistics will be calculated based on the actual number of samples achieved.

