2.2 Primary Hypothesis

Clinicians will rate the T-DOC® 5 Fr vesical and abdominal catheter as safe and effective for measuring urodynamic pressure in at least 95% of enrolled pediatric subjects 12 years of age and younger.

For statistical purposes, this hypothesis will be examined based on the two hypothesis test cases found below. A questionnaire will be presented to the clinician where the clinician's response will be limited to two choices. For example, for the question of safety, the clinician may respond with yes (the device is safe) or no (the device is not safe). Accordingly, a binomial distribution function will be used to evaluate the clinical study results related to the primary hypothesis. Because the alternative hypotheses are directionally based, the null hypotheses will be accepted or rejected based on one-tailed tests. As described in section 4.4 the sponsor team has established that subjects are subjected to no more than minimal risk since an IDE is not required for this study, therefore sample size will be determined based on a desired 95% confidence with 90% reliability.

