12.7 Deviations

In any event there are deviations from the original statistical plan they will be described and justified in the final report.

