Secondary	
To evaluate the usability of the device by collecting clinical user feedback and evaluating the following subjective measures using defined ordinal scales: ease of use, ease of insertion, presence of artefacts, stability of the tracing, perceived time savings, ease of voiding around catheter, presence of use errors and overall satisfaction.	The usability performance endpoint will be captured in a questionnaire format. The trained clinical users will rate the T-DOC® 5 Fr performance on a scale of 1-5 on the study outcome questionnaire.
Exploratory	
To explore whether the newly designed, smaller sized T-DOC® 5 Fr catheters causes undue discomfort based on subjective subject feedback regarding the discomfort and pain level, for those able to communicate such feedback.	This exploratory endpoint will be measured by collecting patient feedback (within the abilities of the child) regarding the level of discomfort and pain experienced during their Urodynamic test using the Wong-Baker visual analogue scale. Patients capable of providing feedback on a Visual Analogue Scale, will grade their discomfort/pain at 5 or lower, on the Wong-Baker scale from 0 ("No Hurt") to 10 ("Hurts worst").
To explore the effect of several factors (e.g., age, gender, weight, height) on optimal insertion depth of the T-DOC® 5 Fr catheters.	Subjects' age, gender, weight, and height will be recorded on TDOC5Fr-PEDS-01-CRF1. These data will be analysed to determine a subject stratification approach to be used in examining further hypotheses for later research regarding optimal insertion depth.

Analysis revisions from the protocol

All subjects enrolled and completed the urodynamic procedure will be considered in the final analysis. Enrolled subjects who do not undergo the urodynamic procedure or begin the urodynamic procedure but do not complete it (for any reason determined by the investigator to be unrelated to the T-DOC® 5 Fr catheters) will not be included in the final analysis and can be replaced.

Primary Endpoint

In the statistical analysis plan, the null hypotheses for the safety and effectiveness endpoints are designed to rule out success rates $\leq 75\%$. The hypotheses as stated in the protocol are based on obtaining a point estimate of $\geq 95\%$ rather than bounding the lowest rate that would be consistent with the observed data.

The allowable Type I error (α) for each hypothesis will be 5% (1-sided), and the Type II error is calculated to be 10% (90% power).

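### The minimum of 28 subjects comes from a zero-failure formula that gives 28.43 (so 29) and that neither success rule matches; the SAP's 90% power cannot be checked

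*Protocol*

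**What the plan says.** Protocol 2.2 sets the basis for the study's size: "sample size will be determined based on a desired 95% confidence with 90% reliability". Protocol 12.4 applies the formula n = ln(1 − confidence)/ln(reliability) and states: "Hence the minimum required number of samples for the primary endpoint is 28 as shown below". It then allows enrolment up to 33 and gives the reason: "The additional subjects will ensure that the desired confidence and reliability levels are met should any data or subjects be disqualified".

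Protocol 12.1 gives the same 90% a second meaning: "Whereas the corresponding Type II error is estimated at 10% (reliability".

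The protocol's decision rule, with a null rate of 95%, is printed for 28 subjects at the end of 12.1.2. The null (the favourable outcome) is "accepted when 25 or more procedures have been rated safe". On the method, Protocol 2.2 says that "a binomial distribution function will be used to evaluate the clinical study results related to the primary hypothesis".

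The SAP (Primary Endpoint) replaces this rule. The null becomes a rate of 75% or less, tested one-sided at 5% for each of safety and effectiveness, and both nulls must be rejected for the study to succeed. On power it says that "the Type II error is calculated to be 10% (90% power". It gives no assumed true rate, no sample size, no named test and no pass mark, and it does not revisit the range of 28 to 33.

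**The concern.** The sample size should follow from the test that decides success. Here it follows from a demonstration formula (no failures seen in n subjects) that neither document uses as a success rule. If so, a passing study need not have the 95%/90% property used to justify its size, and adding subjects does not restore that property once one failure occurs. The printed minimum also seems to have been rounded down, and a proportion (reliability) has been named as an error probability. After the SAP changed the null, the one remaining statement about power has no inputs from which a reader could check it. For a study described as pivotal, the reader should be able to see what 28 to 33 subjects can show.

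**Working it through.** **Inputs.** Confidence 95%, reliability 90%, minimum 28 and maximum 33 (Protocol 12.4); protocol null 95% with pass mark 25/28 (12.1.2); SAP null 75%, one-sided 5% per endpoint. Two inputs are assumptions. The test is taken as exact binomial, because Protocol 2.2 names the binomial distribution and the SAP names no test. The true rate is illustrated at 95% and 96%, because the SAP states none.

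**1. The plan's figure.** ln(0.05)/ln(0.90) = −2.9957/−0.10536 = 28.43. The printed 28 is this value rounded down.
- n = 28: confidence with zero failures = 1 − 0.90^28 = 94.77%; 95% lower bound for 28/28 = 0.05^(1/28) = 89.85%.
- n = 29: 1 − 0.90^29 = 95.29%; lower bound for 29/29 = 0.05^(1/29) = 90.19%.

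**2. What one failure does to the 95%/90% target.** The requirement is P(at most 1 failure | n, failure rate 0.10) ≤ 0.05. At n = 45 the probability is 0.0524; at n = 46 it is 0.0480. So one failure needs 46 subjects. Within the planned range, one failure gives lower bounds of 84.1% (n = 28) to 86.4% (n = 33). Zero failures give 89.85% at n = 28 and 90.2–91.3% at n = 29 to 33.

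**3. The protocol rule (superseded).** P(X ≤ 24 | 28, 0.95) = 0.049 and P(X ≤ 25) = 0.163, so the printed cut-off is correct. It tolerates three failures, and the exact one-sided 95% lower bound for 25/28 is 74.6%.

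**4. The SAP rule.** The pass mark is the smallest r with P(X ≥ r | n, 0.75) ≤ 0.05.

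| n | Pass mark | Attained alpha | Lower bound at pass mark | Power per endpoint at true rate 95% |
|---|---|---|---|---|
| 28 | 26 | 0.0166 | 79.2% | 83.7% |
| 29 | 26 | 0.0455 | 75.4% | 94.5% |
| 30 | 27 | 0.0374 | 76.1% | 93.9% |
| 31 | 28 | 0.0307 | 76.8% | 93.3% |
| 32 | 29 | 0.0252 | 77.5% | 92.6% |
| 33 | 30 | 0.0205 | 78.1% | 91.9% |

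At n = 28, a pass mark of 25 would have alpha 0.0551, just over 5%. That is why power at 28 is lower than at 29.

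**5. Can the 90% be obtained?** Yes. At n = 28 a true rate of 96% gives 90.0% per endpoint. At n = 29 to 33, true rates of about 93.9–94.6% give it.

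**6. Both endpoints.** With per-endpoint power P, joint power lies between 2P − 1 and P whatever the correlation. At a true rate of 95% on both endpoints, this is 67.5–83.7% at n = 28, 89.0–94.5% at n = 29 and 83.8–91.9% at n = 33.

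**7. The label.** The formula contains a confidence level and a proportion but no alternative rate, so it yields no Type II error.

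**The case against.** The case on the other side has real force.

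- **28 or 29 is a small difference.** Confidence moves from 94.8% to 95.3%, and 29 already lies inside the planned range. This stands: taken alone, the rounding changes no decision under the SAP.
- **The 25/28 rule no longer decides anything.** Also true. It matters here only because it shows that the formula did not fit even the rule it was written beside.
- **The extra subjects may be meant only as cover for losses.** They do serve that purpose for the number analysed. But the sentence promises the confidence and reliability levels, and these depend on failures as well as on numbers.
- **A reader might infer that the SAP's 90% power is wrong, or that the study is underpowered.** The documents do not support this. Step 5 shows that 90% per endpoint is attainable within 28 to 33, and 83.7% arises only from an assumed 95% true rate, an assumed exact test and exactly 28 analysed.
- **A reader might infer that joint power must fall below 90%.** That needs further assumptions. The SAP sets its error rates for each hypothesis, so 90% reads naturally as per endpoint. Both ratings concern the same child and procedure, so independence is not an evident default. At n = 29 joint power could be as high as 94.5%. Not stating joint power is a reporting gap.
- **A reader might infer that the SAP will present a pass as 90% reliability.** It does not; it already frames success as a rate above 75%.

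**Conclusion.** The point holds for the protocol's sample-size statement. The printed minimum is one short of what its own formula requires. The formula's zero-failure condition is absent from both success rules, whose lower bounds at the pass mark are 74.6% (protocol, 25/28) and 75.4–79.2% (SAP, n = 28 to 33), against the 90% used to justify the size. The assurance about extra subjects is true only with zero failures and at least 29 analysed. Calling reliability a Type II error is a mislabel. These results follow from the documents' own figures, plus the exact binomial test assumed for the SAP rule.

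For the SAP, the finding is narrower: its 90% power is unverifiable because the true rate, sample size and test are missing. The conditional power figures are illustrations and do not show an error.

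**What to change.** - **Protocol 12.4 (or a note in the final report):** correct 28 to 29, or keep 28 and restate the confidence as 94.8%. Say that the figure comes from a zero-failure formula, and remove the assurance that extra subjects secure the stated levels.
- **Protocol 12.1:** remove the label that equates reliability with Type II error.
- **SAP, Primary Endpoint, one paragraph:** name the exact binomial test, the assumed true rate and the resulting per-endpoint power at the number analysed. If 95% and 28 are used, that power is 83.7%. Give joint power as a range, because the correlation between the two ratings is unknown.
- **Reporting:** give the exact one-sided 95% lower bound for each endpoint, and make no 90% reliability claim unless that bound supports it.
- **Final report:** describe the change of basis, as Protocol 12.7 already requires: "In any event there are deviations from the original statistical plan they will be described and justified in the final report".

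The cost is one SAP paragraph, one number, one label, one sentence and two exact bounds. No new data and no added enrolment are needed.
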